1.2.4. Potential Risks

The following potential risks for Ad26.Mos.HIV and Clade C/ Mosaic gp140 will be monitored during the study and are specified in the protocol:

Risks Related to Vaccination

Subjects may exhibit general signs and symptoms associated with administration of a vaccine, or vaccination with placebo, including fever, chills, rash, myalgia, nausea/vomiting, headache, dizziness, arthralgia, general itching, and fatigue. In addition, subjects may experience local (injection site) reactions such as local itching, warmth, pain/tenderness, erythema/redness, induration/swelling, arm discomfort or bruising of the skin at the injection site. These side effects will be monitored, but are generally short-term and do not require treatment.

Syncope can occur in association with administration of injectable vaccines. Syncope can be accompanied by falls. Procedures should be in place to avoid falling injury. If syncope develops, subjects should be observed until the symptoms resolve. Fear of injection might lead to fainting and fast breathing.

Subjects may have an allergic reaction to the vaccination. An allergic reaction may cause a rash, urticaria or even anaphylaxis. Severe reactions are rare. Medications must be available in the clinic to treat severe allergic reactions. Subjects with a known allergy, or history of anaphylaxis or other serious adverse reactions to vaccines or vaccine excipients will be excluded from the study.

The risks related to vaccine-induced seropositivity (VISP) are discussed in Section 9.4.3.

Based on data with other replication-incompetent adenovirus vector vaccines, the risk of shedding of the Ad26 vector is considered negligible, if any.⁴

Risks Related to Aluminum

Aluminum is one of the most common metals found in nature and is present in air, food, and water. Aluminum salts, such as aluminum hydroxide, aluminum phosphate have been used safely in vaccines for more than 70 years. A few studies have reported an association between vaccines containing aluminum adjuvants and persistent nodules at the injection site, at an estimated rate of 0.03% to 0.83%. ^{29,30,31,32} Two studies examining infant exposure to aluminum from both diet and vaccines concluded that aluminum adjuvants at the levels included in vaccines are well below the calculated safe body burden. ^{33,34} A 2017 review found that current data do not support a causal relationship between aluminum-containing vaccines and a variety of autoimmune disorders. ³⁵

Pregnancy and Birth Control

The effect of the study vaccines on a fetus or nursing baby is unknown, as well as the effect on semen, so women of childbearing potential, and men having sexual intercourse with women, are required to agree to practice adequate birth control measures for sexual intercourse from at least 28 days before the first vaccination (or immediately prior to first vaccination for men) until at least 3 months after the last vaccination (see Section 4.1) of the main study and from at least 28 days

before the late boost vaccination until 3 months after the late boost vaccination (see Section 4.5). Women who are pregnant or breast-feeding, or are planning to become pregnant while enrolled in the main study until 3 months after the last vaccination, will be excluded from enrollment into the main study. In addition, women who are pregnant, breast-feeding or planning to become pregnant from screening for the late boost vaccination until 3 months after the vaccination will not be eligible to receive the late boost vaccination.

Risks from Blood Draws

Blood drawing may cause pain/tenderness, bruising, bleeding, becoming lightheaded, dizziness, vaso-vagal response, and, rarely, infection at the site where the blood is taken.

Risks from Human Leukocyte Antigen (HLA) Testing

Tests results can be used to provide information about how susceptible subjects are to certain diseases. Used inappropriately, this information could be discriminatory (for example, by insurance companies). HLA typing can also be used to determine paternity. However, the blood samples donated will not be used for this purpose; they will be used only to provide study investigators information about the immune system. The results will be coded to protect subject identity.

Unknown Risks

There may be other serious risks that are not known.

Subjects may believe that this vaccine provides protection against acquiring HIV infection, and therefore practice riskier behavior. They will receive extensive counseling throughout the study to address this potential problem. It is not known if the study vaccines increase or decrease the chance of becoming HIV infected when exposed, or if upon becoming HIV infected, the person's disease course progresses faster or slower to AIDS.

In previous HIV-efficacy studies utilizing Ad5, a trend towards increased HIV-1 infection was observed in vaccine recipients as compared with placebo recipients. Ad26 is biologically substantially different than Ad5 and Ad26-based vaccines afford superior protective efficacy compared with Ad5-based vaccines against SIV_{MAC251} challenges in rhesus monkeys. Further, Ad26 did not increase the number or activation status of total or vector-specific CD4⁺ T-lymphocytes at mucosal surfaces in humans following vaccination in a randomized, double-blind, placebo-controlled clinical study.

1.2.5. Overall Benefit/Risk Assessment

Based on the available data and proposed safety measures, the overall benefit/risk assessment for this clinical study is considered acceptable for the following reasons:

Preliminary safety data from the ongoing clinical studies and safety data generated with the related vaccines containing different inserts revealed no significant safety issues (see Section 1.1.2.1).

- Only subjects who meet all inclusion criteria and none of the exclusion criteria (specified in Section 4) will be allowed to participate in this study. The selection criteria include adequate provisions to minimize the risk and protect the well-being of subjects in the study.
- Safety will be closely monitored throughout the study:
 - After each vaccination, subjects will remain in the clinic and be closely observed by study staff for at least total 30 minutes post-vaccination, or longer if deemed necessary by the investigator, to monitor the development of any acute reactions. Any unsolicited, solicited local or systemic adverse events will be documented during this period. Subjects will use a diary to document solicited local and systemic AEs in the evening after each vaccination and then daily for the next 7 days at approximately the same time each day.
 - Subjects will undergo safety follow-up by study staff 24-72h after each vaccination in the main study, by telephone, email or clinic visit.
 - The investigator or the designee will document unsolicited AEs, SAEs and (potential) adverse events for special interest (AESIs) as indicated in section 12.3.1.
 - Safety evaluations, including physical examinations, vital sign measurements, clinical safety laboratory testing (performed at screening, pre-dose, 2 weeks after each dose and at Weeks 36, 60 and 72 of the main study) and pregnancy testing (prior to each vaccination), will be performed at scheduled visits during the study. In addition, a symptom-directed physical examination, vital sign measurements and pregnancy testing will be performed at screening for the late boost vaccination.
 - Any clinically significant abnormalities (including those persisting at the end of the study/early withdrawal) will be followed by the investigator until resolution or until a clinically stable endpoint is reached (see Section 12.3.2).
- Several safety measures are included in this protocol to minimize the potential risk to subjects, including the following:
 - Since this is a first in human study of Mosaic gp140, enrolment will be paused after the first 6 subjects have received their third vaccination (first vaccination with Mosaic gp140, depending on assignment), the Protocol Safety Review Committee (PSRT) and Principal Investigators have reviewed blinded safety data collected 1 day after vaccination and established that there are no concerns.
 - For all subjects, there are pre-specified rules that would result in pausing of further vaccinations if predefined conditions occur, preventing exposure of new subjects to study vaccine until the PSRT and/or DRC reviews all safety data (see Section 11.9).
 - Subjects will discontinue study vaccine for the reasons included in Section 10.2.
 - Confirmed HIV infection will be monitored as an AESI.
 - From the time of local regulatory approval of protocol amendment 5 onwards, TTS will be monitored as an AESI. Thrombotic events and/or thrombocytopenia are considered to be potential AESIs.

- If acute illness (excluding minor illnesses such as diarrhea or mild upper respiratory tract infection) or fever (body temperature ≥38.0°C) occur at the scheduled time for vaccination, the subject may be vaccinated within the window allowed for the scheduled vaccination.
- Contraindications to vaccination are included in Section 10.3.

1.3. Overall Rationale for the Study

The proposed clinical study in healthy HIV-uninfected subjects will evaluate the safety/tolerability and the immunogenicity of 2 different prime/boost regimens: priming with Ad26.Mos4.HIV and boosting with Ad26.Mos4.HIV and either Clade C gp140 plus adjuvant or a combination of Clade C and Mosaic gp140 plus adjuvant. The goal of this study is to evaluate if the addition of Mosaic gp140 to Clade C gp140 improves the breadth of humoral immune responses (defined as immune recognition of diverse strains/clades of HIV), which will ultimately assist in the selection of the best regimen(s) for evaluation in future efficacy studies.

To assess the durability of the immune responses, a Long-term Extension (LTE) phase of approximately 3 years was introduced for subjects randomized to Group 1 or Group 2, who have received all 4 vaccinations and are negative for HIV infection at the end of the main study. The vaccination regimens of Group 1 and Group 2 (including Ad26.Mos4.HIV and either Clade C gp140 alone or combined with Mosaic gp140) form the basis for the regimens that will likely be evaluated in future studies.

In addition, subjects enrolled in the LTE phase will be offered participation in an extension of the LTE phase. Eligible subjects who consent to participation will be randomized (3:1 ratio) to receive a boost vaccination with Ad26.Mos4.HIV together with bivalent gp140 or placebo at Week 192 (-4 weeks/+4 months [Visit 22a], ie, approximately 3 years after the 4th vaccination of the primary vaccination series). The goal is to evaluate the impact of a late boost vaccination on the quantity (including magnitude and breadth) and quality of the immune response (humoral and cellular) as well as the safety of such late boost vaccination.

2. OBJECTIVES, ENDPOINTS, AND HYPOTHESIS

2.1. Objectives and Endpoints

Objectives		Endpoints		
Primary		_		
To assess safety/tolerability of the differe vaccine regimens	nt •	Solicited local and systemic adverse events (AEs) for 7 days after each vaccination.		
	•	AEs for 28 days after each vaccination.		
	•	Discontinuations from vaccination/from study due to AEs.		
	•	Serious adverse events (SAEs) and AEs of special interest (AESIs) of confirmed HIV infection during the course of the study, including the LTE phase.		

Objectives	Endpoints
• To assess Envelope (Env)-binding antibody (Ab) responses of the 2 different vaccine regimens.	Env-specific binding Abs (titers and breadth).
To assess safety/tolerability of a late boost vaccination.	Solicited local and systemic AEs for 7 days after the late boost vaccination.
	• AEs for 28 days after each the late boost vaccination.
	 SAEs and AESIs of confirmed HIV infection until the end of the study.
	AESIs of TTS for 6 months after the late boost vaccination
Secondary (applicable to main study, LTE and late	boost vaccination)
• To assess neutralizing Ab (nAb) responses,	• Env-specific nAbs (titers and breadth)
Ab functionality (as assessed by phagocytosis), and Ab isotyping.	• Env-specific functional Abs (phagocytosis score and breadth).
	• Env-specific binding Ab isotypes (immunoglobulin (Ig)A, IgG1-4) (titers and breadth).
To assess T-cell responses.	 Interferon gamma (IFNγ) peripheral blood mononuclear cell (PBMC) responders to mosaic and potential T-cell epitopes (PTE) peptide pools of Env/group-specific antigen (Gag)/polymerase (Pol).
	 Cluster of differentiation (CD)4+ and CD8+ T-cell functionality (% cells producing ia, IFNγ, interleukin 2 (IL-2), IL-4, tumor necrosis factor α [TNFα]).
	 T-cell development with emphasis on follicular helper T- cells and memory differentiation.^d
Exploratory (applicable to main study, LTE and lat	e boost vaccination)
• To explore whether the adenovirus serotype 26 (Ad26) vector is shed after vaccination.	 Polymerase chain reaction (PCR) positive for Ad26 sequences (urine and mid-turbinate swab).
To explore Ab functionality (other than phagocytosis).	• Ab functionality evaluation (such as Ab-dependent cellular cytotoxicity [ADCC], Ab-dependent complement deposition [ADCD]; excluding phagocytosis (ie, Ab-dependent cellular phagocytosis [ADCP]).
• To explore Ab Fc characterization.	• Ab Fc (sub)typing.
• To explore T-cell and Ab epitope mapping.	• Epitope mapping of Ab to Env and T-cell responses to Gag/Pol/Env (PTE and vaccine peptide pools).
To explore gene expression patterns using PBMCs.	 Regulation of genes (or clusters) that predict specific immune responses and human leukocyte antigen (HLA) typing.
To explore B-cell responses.	Ab-producing B-cells and characterization of B-cell memory development.
To explore immune responses against the viral vector.	Ad26 nAbs (titer).

^d The follicular helper T-cells and memory differentiation was included as secondary objective for the main study. Due to difficulty qualifying the assay for these specific markers, these T-cell responses will be considered as an exploratory objective for the late boost vaccination.

	Objectives		Endpoints	
•	To explore the social impact of participation in an HIV-vaccine study for subjects via a social impact questionnaire.	•	Social impact.	
•	To explore durability of the immune responses to the vaccine regimens in the groups selected for the Long-term Extension (LTE) phase.	•	Available samples from time points during the LTE phase will be used for determination of long-term durability of the immune responses.	

In addition, following exploratory objectives are applicable to the late boost vaccination only:

	Objectives		Endpoints		
•	To assess Env-binding antibody Ab responses following late boost vaccination approximately 3 years after receiving the 4 th vaccination of the primary vaccination series.	•	Env-specific binding Abs [ELISA] at 3, 7 or 14 ^e days and 28 days post late boost vaccination (titers and breadth).		
•	To explore the role of Ad26 neutralizing antibodies on the immune response to a late boost vaccination.	•	Ad26 neutralizing antibodies at the time of vaccination relative to the immune response as evaluated by ELISA.		
•	To compare the immune response to late boost vaccination with a vaccine matched to the primary vaccination series (Group 2) vs a closely related vaccine (Group 1).	•	Relative ELISA magnitudes between groups randomized to Group 1 vs Group 2 in the main study.		
•	To evaluate whether humoral responses induced by a late boost vaccination are able to mediate protection in non-clinical passive transfer studies.	•	Analysis of protection against HIV-related challenge viruses, such as simian human immunodeficiency virus (SHIV), in a suitable animal model, and/or in vitro.		

See Section 9 for evaluations related to endpoints.

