Subjects enrolled in the LTE phase will be offered participation in an extension to the LTE phase to investigate the safety and immunogenicity of a late boost vaccination approximately 3 years after the last vaccination in the main study (depending on availability of IRB and HA approvals per country/site regulations). Assessment of participants' eligibility for the late boost vaccination and vaccination itself will occur within 4 weeks prior to Week 192 until 4 months after Week 192 (Visit 22a, which can be split over several visits). Eligible, consenting subjects will be randomly assigned (3:1 ratio, see Table 2 below) in a blinded fashion to active vaccination with Ad26.Mos4.HIV and bivalent gp140 (Group 1b) or placebo (0.9% saline) (Group 2b). The aim is to have at least 48 participants enrolled in the late boost extension. Randomization will be stratified by region (USA, East Africa: assuming sufficient numbers from Rwanda in the LTE phase) and by group randomized to in the main study (Group 1/Group 2). Upon receipt of the late boost vaccination, participants will be followed up for immunogenicity and safety for a further 12 months or, if they consent to longer follow-up, 24 months. Unblinded interim data analysis (sponsor unblinding only) will be performed approximately 4 weeks after the last subject received the late boost vaccination. LTE subjects declining participation or not eligible for participation in the late boost extension will complete the study at Visit 23 of the LTE phase.

The duration of the subject's participation will be approximately 78 weeks (6-week screening + 72 weeks main study) for subjects not participating in the LTE phase and approximately 222 weeks for subjects participating in the LTE phase but not receiving a late boost vaccination and approximately 246 (12-month follow-up) or 294 (24-month follow-up) weeks for subjects receiving a late boost vaccination.

After vaccination, subjects will remain under observation at the study site for at least 30 minutes for presence of any acute reactions and solicited events. In addition, subjects will record solicited events in a diary for 7 days post-vaccination as described in Section 9.1.1. See Section 12.1.3 for grading of severity of solicited AEs. From the time of local regulatory approval of protocol amendment 5 onwards, TTS is considered to be an AESI. Thrombotic events and/or

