Based on the primary analysis of HPX2003 and HPX2004, the combination of aluminum phosphate-adjuvanted Clade C gp140 and Mosaic gp140 was selected for inclusion in the 3rd and 4th vaccinations over the Clade C gp140 alone for use in Phase 3. In line with the bivalent nature of the Env and Gag-Pol encoding Ad26 vectors, a bivalent mixture of gp140 proteins, which have complementary sequences, is anticipated to provide improved immunological coverage of the circulating strains of HIV-1 globally, than either component alone. The favorable safety profile of Clade C gp140 was maintained by replacing half of the Clade C gp140 dose with Mosaic gp140, while maintaining the same total glycoprotein dose of 250 mcg (corresponding to a total protein dose of 155 mcg). Peak immune responses at Month 7, post 3rd vaccination were highly comparable between the 2 regimens and similar levels of Clade C specific humoral and cellular responses were observed, demonstrating that the regimen containing the bivalent protein formulation is globally relevant. The immune responses induced by the combination of Clade C gp140 and Mosaic gp140 show broad Env-specific binding and functional humoral responses, as well as high frequencies of Env-specific T cell responses and improved Clade B Env-binding antibody responses without compromising Clade C Env-binding antibody responses. In addition, a combination of Clade C and Mosaic gp140 is preferred due to the efficient manufacturability of Mosaic gp140, which results in higher yields compared to Clade C gp140.

The Month 13 (Week 52; 4 weeks post 4th vaccination) analysis results of HPX2003 strengthened the original choice of the combination of aluminum phosphate-adjuvanted Clade C gp140 and Mosaic gp140 over the Clade C gp140 alone. After completion of the vaccination series, the Clade C responses were still comparable between regimens while the combination of Clade C gp140 and Mosaic gp140 improved responses beyond Clade C. The geometric mean ratio (GMR) and 95% CI of binding antibody levels induced by the bivalent relative to the Clade C alone regimen for Clade B and Mos1 (2.1 [1.7 - 2.7] and 1.4 [1.1 - 1.9], respectively) after completion of the vaccination series (Figure 1) significantly improved from the Clade C alone regimen.

Figure 1: GMR (95% CI) of the Clade C+ Mos gp140 /Clade C gp140 Groups (Pooling VAC89220HPX2003-VAC89220HPX2004)

Geometric Mean Ratio (95% CI) at Week 52

[GIMHUMCEL99A.RTF]

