5. TREATMENT ALLOCATION AND BLINDING

Treatment Allocation

Procedures for Randomization

Central randomization will be implemented in this study. In the main study, subjects will be randomly assigned to 1 of 3 treatment groups based on a computer-generated randomization schedule prepared before the study by or under the supervision of the sponsor. The randomization will be balanced by using randomly permuted blocks and stratified by region. Similarly, subjects eligible for the late boost vaccination will be randomly (3:1 ratio) assigned to active vaccine or placebo. The randomization will be balanced by using randomly permuted blocks and stratified by region (USA, East Africa: assuming sufficient numbers from Rwanda in the LTE phase) and by group randomized to in the main study (Group 1/Group 2).

The interactive web response system (IWRS) will assign a unique treatment code, which will dictate the treatment assignment and matching study vaccine for the subject. The requestor must use his or her own user identification and personal identification number when contacting the IWRS, and will then give the relevant subject details to uniquely identify the subject.

Blinding

The subjects, study-site personnel (except for those with primary responsibility for study vaccine preparation and dispensing), and investigator will be blinded to study vaccine allocation of the main study until Week 72, with the exception of the partial unblinding for the start of the LTE phase (see below). The sponsor will be blinded to study vaccine allocation until the primary (Week 28) analysis (see Section 11.6).

The pharmacist with primary responsibility for vaccine preparation (see Section 14.3) will not be blinded to the study vaccine. In order to preserve blinding, he/she will place an overlay on the syringes. Administration of study vaccine to the subjects can be performed by a qualified healthcare provider from the study site (including the pharmacist who prepared the study vaccine) who will have, on the day of administration, no other study function related to safety, study data evaluation or recording of AEs for those subjects that he/she vaccinated on that day.

The investigator will not be provided with randomization codes. The codes will be maintained within the IWRS, which has the functionality to allow the investigator to break the blind for an individual subject.

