After re-check of inclusion/exclusion criteria, abbreviated, symptom-directed physical examination (including weight measurement), measurement of vital signs, and a urine pregnancy test (for women of childbearing potential), eligible subjects will be randomized as described in Section 5. If the vaccination occurs on the same day as the screening, the pre dose vital signs assessment and physical examination do not need to be repeated.

If medical status and/or physical examination suggest(s) significant changes have occurred since screening, the clinically relevant screening assessments will be repeated and the vaccination visit rescheduled, provided that the rescheduled visit is within 42 days of the initial screening assessment and all screening assessments and vaccination are still possible within the -4 week/+4 month time window around Visit 22a (Week 192).

Pre-dose samples for immunogenicity will be collected.

Pre- and post-dose AEs (including SAEs, AEs leading to treatment discontinuation, and AESIs [confirmed HIV infection and TTS]) will also be collected, together with information about any concomitant medications. If the vaccination occurs on the same day as the screening pre-dose AEs will only be collected once.

Study vaccine will be prepared by the site pharmacist, who will place an overlay on the syringes (to preserve blinding) and will send it to the clinic. Administration of study vaccine to the subject can be performed by a qualified healthcare provider from the study site (including the pharmacist who prepared the study vaccine) who will have, on the day of administration, no other study function related to safety, study data evaluation or recording of AEs for those subjects that he/she vaccinated on that day.

After the late boost vaccination, subjects will remain under observation at the study site for at least 30 minutes for presence of any acute reactions and solicited events (see Section 9.3), and vital signs measurement will be repeated.

Subjects will be provided with a thermometer, ruler, and subject diary to measure and record solicited events for 7 days post-vaccination (day of vaccination and the subsequent 7 days).

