### **2.3.3. Late Boost Analysis Set**

The Late Boost (LB) population consists of all subjects from per protocol immunogenicity analysis set who received the late boost vaccination (at least one of the two injections administered at the late boost visit).

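### The late-boost comparison of Group 1 with Group 2 has no pre-boost reference, so any difference left from the primary series would be read together with the response to the boost.

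*Protocol*

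**What the plan says.** **Objective and endpoint.** Among the exploratory objectives that apply only to the late boost, Protocol 2.1 lists one that opens "To compare the immune response to late boost vaccination with a vaccine matched to the primary vaccination series (Group 2" and sets this against a closely related vaccine for Group 1. The paired endpoint is "Relative ELISA magnitudes between groups randomized to Group 1 vs Group 2 in the main study". The synopsis repeats it. No pre-boost reference and no late-boost arm is named.

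**Design.** Under Protocol 5, "subjects eligible for the late boost vaccination will be randomly (3:1 ratio) assigned to active vaccine or placebo", stratified by region and by main-study group. Protocol 3.1 says "The aim is to have at least 48 participants enrolled in the late boost extension". On the vaccination day, "Pre-dose samples for immunogenicity will be collected" (Protocol 9.1.10).

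**SAP.**
- Section 2 sets baseline as the last assessment before the first dose of the study.
- Section 2.3.3 defines the Late Boost set as per-protocol subjects "who received the late boost vaccination (at least one of the two injections administered at the late boost visit"), with no condition on arm.
- Section 6.1 carries the main-study rules over to the late-boost data.
- Section 6.3 compares the two main-study regimens by a geometric mean ratio (GMR) with 95% CI and a t-test or Wilcoxon test, without a covariate.
- Section 4.2 splits late-boost subjects by earlier regimen, but only for disposition.

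**Known difference.** Protocol 3.2 gives Week 52 ratios of bivalent to Clade C alone, pooled over this study and HPX2004: 2.1 (1.7 to 2.7) for Clade B and 1.4 (1.1 to 1.9) for Mos1. It calls the Clade C responses comparable.

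**The concern.** The objective is about response to the boost; the endpoint is about level after it. The two agree only if the groups enter the boost with equal titres. If Group 2 enters higher to some antigen and the boost multiplies titres equally in both groups, the post-boost ratio returns the old ratio instead of 1, and a reader could credit it to matching. The SAP's fold increases do not help, because they are taken from before Dose 1 and so span the primary series and the boost together.

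A second gap is that the groups are defined only by main-study randomization. Each contains late-boost active and placebo recipients, and the text does not say which are compared.

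**Working it through.** **1. The plan's own figure.** Protocol 11.3 states a detectable difference of about 1.85-fold with 90 vs 22 evaluable, SD 0.4 log10, two-sided 5% and 80% power. SE = 0.4 × √(1/90 + 1/22) = 0.0951; 10^[(1.960 + 0.842) × 0.0951] = 1.847. It reproduces. No figure is given for the late boost.

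**2. Late-boost sizes (assumed).** Take 48 subjects, randomized 3:1, with the main-study split of 25:100 retained. That gives 36 active, about 7 vs 29, and about 10 vs 38 with placebo included. For 7 vs 29, SE = 0.4 × √(1/7 + 1/29) = 0.168, and the detectable fold is 10^(2.80 × 0.168), about 3.0.

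**3. Chance of p<0.05 with no true boost difference.** Two-sided t-test, 34 df, noncentrality = log10(ratio)/0.168:

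| Ratio remaining after the boost | Noncentrality | P(p<0.05) |
|---|---|---|
| 1.2 | 0.0792/0.168 = 0.47 | 7% |
| 1.4 | 0.1461/0.168 = 0.87 | 13% |
| 2.1 | 0.3222/0.168 = 1.91 | 46% |

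**4. How much would carry through.** The last two rows assume that the whole Week 52 ratio survives to Week 192 and then passes multiplicatively through the boost. Two alternatives start from 2.1 just before the boost:
- *Imperfect pre/post correlation* (simulation, 1,500 runs, group acting only through the pre-boost titre). At correlations of 0.3, 0.5, 0.8 and about 1, the raw ratio is 1.23, 1.46, 1.84 and 2.10, with rejection of 8%, 15%, 35% and 46%. The closed form 2.1^ρ gives 1.25, 1.45 and 1.81 for the first three, so the simulation agrees within its noise.
- *Equal absolute increment* of 1, 3 or 10 times the Group 1 pre-boost titre. (2.1 + A)/(1 + A) = 1.55, 1.28 or 1.10. By the formula in step 3, rejection is 20%, 9% or 6%.

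**5. Adjustment.** In the same simulations, ANCOVA on pre-boost log10 titre gave a GMR of 0.98 to 1.01 and about 5% rejection throughout. Fold-rise over-corrected when the correlation was below 1: 0.59 to 0.87 for a starting ratio of 2.1 and correlations of 0.3 to 0.8.

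**6. If placebo recipients were pooled.** Stratification keeps their share near 25% in each main-study group. A true boost ratio of 2.0 shrinks to 2^0.75 = 1.68. The SD becomes √(0.16 + 0.75 × 0.25 × log10(rise)²) = 0.450, 0.502 or 0.589 for 3-, 5- or 10-fold rises. But n also grows to 10 vs 38. The 95% CI half-width for active recipients only is 2.032 × 0.168 = 0.342. Pooled, it is 2.013 × SD × √(1/10 + 1/38) = 0.322, 0.359 or 0.422, which is 6% narrower, 5% wider or 23% wider.

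**The case against.** **A Week 192 difference is assumed.** This stands. The Week 52 ratios were measured 140 weeks earlier and pooled over two studies, and no Week 192 titres are given. Clade C was comparable, so the point concerns Clade B and Mos1. A reader might infer that the groups are known to differ before the boost; the documents do not show that.

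**Placebo pooling is not planned in so many words.** This also stands. The Protocol's definitions describe the late boost as the active product, and saline is neither a matched nor a related vaccine. On the other side, Protocol 3.2 and SAP 5 use the term for both arms, and SAP 2.3.3 sets no arm condition. That is an ambiguity to close. A reader might infer that pooling biases the comparison; with randomization stratified by main-study group, it dilutes it.

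**The data would still be visible.** SAP 6.3 tabulates geometric means by group at each time point, and a pre-dose sample is drawn at Visit 22a, so a leftover ratio could be noticed. It would not be taken out of the comparison.

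**Adjustment changes the question.** Main-study regimen affects the pre-boost titre. The raw ratio is a legitimate total effect of primary regimen plus boost. ANCOVA conditions on a measurement made after randomization and is open to confounding, for example by general immune responsiveness. The simulation's value near 1.0 follows from its own premise that group acts only through the pre-boost titre. So the adjusted analysis belongs beside the raw one and should not replace it.

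**It is exploratory.** No formal hypothesis is tested and no decision rule depends on it. The effect is on interpretation.

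**Conclusion.** The point holds in a limited form. The endpoint has no pre-boost reference, the SAP supplies none, and the analysis as written cannot by itself distinguish carry-over from response to the boost.

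With 7 vs 29 actively boosted and SD 0.4, the chance of a nominally significant result with no true boost difference runs from about 6-8% (ratios of 1.10 to 1.23 left after the boost) to 13% (1.4) or 46% (2.1). A reader might take 46% as the general false-positive rate. It applies only to Clade B, with the whole Week 52 ratio persisting for 140 weeks and then carried through multiplicatively. The sizes assume 48 enrolled with the 1:4 split retained, and the SD is borrowed from the main-study calculation.

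The unstated restriction to active recipients is a lesser matter: at most a contrast diluted from 2.0 to about 1.68, with interval width changed by -6% to +23% for 3- to 10-fold rises. The change is worth making because the sample needed is already drawn.

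**What to change.** In Protocol 2.1 and SAP 6.3:
1. State that this comparison uses late-boost active recipients (Group 1b), classified by main-study Group 1 or Group 2.
2. Keep the unadjusted post-boost GMR. Beside it, report the Visit 22a pre-dose geometric mean for each main-study group.
3. Add the Group 2/Group 1 GMR of post-boost log10 titre, adjusted for the Visit 22a pre-dose log10 titre to the same antigen, with 95% CI. Give fold-rise from Visit 22a as a sensitivity analysis.
4. Say that the unadjusted ratio reflects primary regimen plus boost, and that the adjusted one conditions on a titre measured after main-study randomization.

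No new visit or sample is needed; the cost is wording and analysis. The downside is one more covariate with about 7 subjects in the smaller group, and an adjusted estimate that remains exploratory.
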